#### **10.4 Interim analysis (if applicable)**

An interim analysis will be performed after 50% of the participants needed has been accrued/included. The analysis will focus on the primary outcome and on safety. The non-inferiority design of the study means that a clear disadvantage of the PCT-guided treatment arm or in other words a clear benefit of the usual care arm will lead to discontinuation of the trial. The p-value at the interim analysis will be 0.0054 according to the O'Brien-Fleming method, and the p-value at final analysis will be 0.0492 (27). The safety data consists of observed adverse events and SAE. The change of the p-value at final analysis will lead to an increase of 2 patients per treatment arm. The number of patients per treatment arm will be 315. Using a 10% drop-out rate this will lead to a total number of patients of 693.

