Plan for statistical analysis	
Primary analysis The primary endpoint is defined as 30-day treatment failure. The per protocol (PP) population is the main analysis population. The difference and corresponding 95% confidence interval (two-sided) in the incidence of the primary endpoint between the randomly allocated strategies (biomarker-guided antibiotic use minus usual care) will be determined. Non-inferiority will be concluded if the upper limit of this confidence interval does not exceed the prespecified non-inferiority margin of 5%.
 
Secondary analyses Differences in the incidence of these secondary endpoints between randomly allocated strategies will be analyzed by chi-square tests and logistic regression.

---

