### **Statistical and analytical plans**

#### **Primary analysis**

The primary endpoint is defined as 30-day treatment failure. The per protocol (PP) population is the main analysis population. An analysis will be performed for the randomly

---

allocated antibiotic strategy (i.e. usual care versus antibiotics in patients with PCT >0.25 µg/L). The difference and corresponding 95% confidence interval (two-sided) in the incidence of the primary endpoint between the randomly allocated strategies (biomarker-guided drug use minus drug-in-all) will be determined. Non-inferiority will be concluded if the upper limit of the 95% confidence interval does not exceed the prespecified non-inferiority margin of 5%.

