8.5.1 Purpose of Interim Analyses

An interim analysis will be performed because of uncertainty about the safety of the PCT-guided treatment strategy. Subjects who will not receive antibiotic therapy in the presence of a bacterial infection (because of a false-low/negative PCT concentration) could deteriorate because of the withholding of antibiotic treatment. This could lead to adverse outcomes, such as longer duration of hospital stay, ICU admission or death.

Another reason for performing the interim analyses is the possibility of a significant evidence of benefit of the PCT-guided treatment strategy according antibiotic treatment. A significant reduction in treatment failure could also mean a significant reduction in ICU admission, need for non-invasive ventilation, readmission, re-exacerbation and death.

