8.5.3 Stopping Rules

Criteria on which the DSMB may decide to terminate the trial prematurely are:

1. Any serious adverse event related to the treatment under investigation has occurred.
2. A significant evidence of benefit

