8.6 Multiple Testing

Op dit moment niet van toepassing, mogelijk nog wanneer primair eindpunt zou veranderen.

9 Summary of Study Data

Table 1. Baseline characteristics

The baseline characteristics are given in the table below.

	Usual care (n = 308)	PCT-guided treatment (n = 308)
Age in years – mean±SD		
Male gender – no. (%)		
BMI – mean±SD		
Smoking status: - current – no. (%) - past – no. (%) - pack years (mean, range)		
FEV1 % predicted - mean±SD		
GOLD classification: - I – no. (%) - II – no. (%) - III – no. (%) - IV – no. (%)		
Exacerbation type: - type I – no. (%) - type II – no. (%) - type III – no. (%)		
Median duration of symptoms in days - mean±SD		
CRP in mg/L – median [IQR]		
WBC 10 ⁹ /L – mean±SD		
CAT score – median [IQR]		
EXACT- RS score – median [IQR]		

Primary outcome

The primary outcome will be treatment failure within 30 days. A non-inferiority margin of 5% will be used to assess non-inferiority. Treatment failure is defined as disease-related mortality, endotracheal intubation, vasopressors, renal failure, lung abscess/empyema, development of pneumonia and hospital readmission within 30 days.

- Binary outcome parameter: yes or no. Description: number and percentage.
- To account for the multicenter effect a logistic mixed effects model will be estimated with

centers as random effect and treatment group as fixed effect to analyze the primary outcome. The risk of primary endpoint in the PCT guided treatment arm versus the usual care treatment arm will be reported with an odds ratio from the logistic model, with a 95% confidence interval. Based on this CI we will determine non-inferiority of the treatment.

Secondary outcome parameters

Skewed data will be analyzed using non-parametric tests. Paired measurements will be analyzed using paired tests.

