10.1 Primary Efficacy Analysis

The summary statistics will be produced in accordance with section 9.

The non-inferiority of the treatment will be decided based on the 95% confidence interval of the OR from the logistic mixed model for the treatment arm versus the usual care arm.

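### The adjusted final level of 0.0492 does not reach any non-inferiority rule, the interim hypothesis is not stated, and 693 patients do not leave 315 per arm after 10% loss

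*Protocol*

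**What the plan says.** **Levels.** Protocol 10.4, repeated in SAP 8.5.5: "The p-value at the interim analysis will be 0.0054 according to the O'Brien-Fleming method, and the p-value at final analysis will be 0.0492". Both sections add 2 patients per arm for the changed final level, giving 315 per arm, and reach a total of 693 with 10% drop-out. Protocol 4.4 sets a one-sided error of 0.025.

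**Decision rules.** There are four, and none mentions 0.0492.
- Protocol synopsis, after specifying a two-sided 95% interval for the risk difference: "Non-inferiority will be concluded if the upper limit of this confidence interval does not exceed the prespecified non-inferiority margin of 5" percent.
- Protocol, Statistical and analytical plans, Primary analysis: "Non-inferiority will be concluded if the upper limit of the 95% confidence interval does not exceed the prespecified non-inferiority margin of 5" percent.
- SAP section 9, Primary outcome, on the 95% interval of an odds ratio: "Based on this CI we will determine non-inferiority of the treatment".
- SAP 10.1: "The non-inferiority of the treatment will be decided based on the 95% confidence interval of the OR from the logistic mixed model".

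**Interim.** Protocol 10.4 and SAP 8.5.5 say that "a clear benefit of the usual care arm will lead to discontinuation of the trial". Protocol 9.5 and SAP 8.5.3 list two other grounds: a treatment-related serious adverse event, and "A significant evidence of benefit". SAP 8.5.1 adds: "Another reason for performing the interim analyses is the possibility of a significant evidence of benefit of the PCT-guided treatment strategy", and explains this as a reduction in treatment failure.

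**Meaning of 693.** Protocol 10.4 and 11.2 use it as the number enrolled. SAP 8.1 uses it as the number who have completed 30-day follow-up. Protocol 8.5 provides for no replacement once the randomisation quota is reached.

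**The concern.** There are three linked problems.

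1. The sample size assumes one final threshold and the decision rules use another. SAP 8.5.5 is headed as an adjustment of confidence intervals but gives no adjusted interval. A confirmatory threshold that exists in two versions leaves a choice open after the results are known.

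2. The stopping grounds point in different directions (harm in one place, benefit in others), and 0.0054 is not tied to a null value, a direction or a sidedness. Which correction is right depends on this. An early look that can yield a non-inferiority claim spends non-inferiority error. A look that can stop only for harm or for superiority spends practically none.

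3. Adding 10% to the required number is not the same as allowing for a 10% loss, so the design does not deliver the 315 per arm it states. Read literally, the SAP 8.1 trigger cannot be met under the plan's own drop-out assumption.

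**Working it through.** **Inputs.** Failure rates 20.4% (usual care) and 16.7% (PCT-guided), margin 5 points, power 80%, one-sided 0.025 (protocol 4.4). Levels 0.0054 and 0.0492, look at 50%, 315 per arm, 10% drop-out, total 693 (protocol 10.4). The levels are read as two-sided, because 0.0492 is set against a two-sided 95% interval and, taken that way, reproduces the plan's sample size.

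**Reproducing the plan's sizes.** With unpooled variance, n per arm = (z_α + z_0.80)² × V / d², where
- V = 0.204 × 0.796 + 0.167 × 0.833 = 0.3015
- d = 0.05 + (0.204 − 0.167) = 0.087

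| Two-sided final level | z_α | n per arm |
|---|---|---|
| 0.05 | 1.960 | 312.6 → 313 |
| 0.0492 | 1.967 | 314.2 → 315 |
| 0.0490 | 1.969 | 314.6 |
| 0.0480 | 1.977 | 316.5 |

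The first two rows match the plan's 313 and 315, so 0.0492 drives the sample size. It is missing only from the decision rules.

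**Overall error if the interim can support a non-inferiority claim.** The two test statistics are bivariate normal with correlation √0.5. The one-sided error is 1 − P(Z₁ < c₁, Z₂ < c₂).

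| Interim / final level (two-sided) | Overall one-sided error |
|---|---|
| 0.0054 / 0.0492 | 0.0256 |
| 0.0054 / 0.05 (plain 95% interval) | 0.0260 |
| 0.0052 / 0.0480 | 0.0250 |
| 0.0031 / 0.0490 | 0.0250 |

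If 0.0054 is kept, the final level that holds 0.025 is 0.0479.

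**Overall error if the interim tests superiority.** At the edge of the non-inferiority null (25.4% v 20.4%, 157 per arm at the look), the chance of crossing 0.0054 in favour of the PCT arm is about 0.00006. The overall one-sided error is 0.0246 with a final level of 0.0492 and 0.0250 with a 95% interval. A stop for harm only cannot raise the non-inferiority error at all.

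**Effect on the interval.** At 315 per arm the standard error is √(0.3015/315) = 3.094 points. Half-widths are 6.06 points at 95%, 6.08 at the 0.0492 level and 6.12 at the 0.0480 level. The choice of level therefore changes the conclusion only if the upper limit lies within about 0.02 to 0.05 points of the margin.

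**Drop-out.**
- 630 × 1.10 = 693, the plan's figure.
- 693 × 0.90 = 623.7, or about 312 per arm. This is below 315, and below the unadjusted 313.
- 630 / 0.90 = 700.
- 1 − 630/693 = 9.1%, the loss that 693 does cover.
- 693 / 0.90 = 770, the enrolment needed if 693 must complete.

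Power = Φ(0.087/√(0.3015/n) − z_α). At 312 per arm it is 79.9% at 0.05, 79.7% at 0.0492 or 0.0490, and 79.4% at 0.0480. At 315 per arm and 0.0492 it is 80.1%.

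**Odds-ratio rule.** A 5-point margin equals an odds ratio of (0.254/0.746)/(0.204/0.796) = 1.33 at the planned control rate. At assumed control rates of 15% and 25% it equals 1.42 and 1.29. The SAP's odds-ratio interval therefore has no fixed counterpart to the margin, whatever its confidence level.

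**The case against.** The best reply is that the plan never says the interim can support an early non-inferiority claim. Harm and benefit are both described as differences between arms, and SAP 8.5.1 explains benefit as fewer failures. On that reading every stated rule holds its error rate and 0.0492 is merely conservative. This is a reasonable reading, and the error excess above applies only on the other one. But no section commits to either. On the superiority reading the 0.0492 and the extra 2 patients per arm serve no purpose, so the text needs a change either way.

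SAP 8.5.5 could also be read as a specific provision that overrides the general 95% in the rules. It does not say so, and SAP 10.1 states 95% outright.

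On size, the objection stands. Seven patients separate 693 from 700, and power moves by less than half a point. The per-protocol population, which is primary, will remove further patients, so 3 per arm will not decide the delivered power.

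SAP 8.1 still carries template instructions, and its trigger probably means that the enrolled 693 have passed day 30. That may be the intent, but as written it conflicts with 693 as the enrolment total.

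**Conclusion.** The concern holds in all three parts, and its numerical effect is small. The final level of 0.0492 enters the sample size but none of the four decision rules. The 0.0054 has no stated null value or sidedness. A 10% loss from 693 leaves about 312 per arm, not 315.

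The worst-case overall error is 0.0260 one-sided against 0.025, and it arises only if the interim can support a non-inferiority claim. The shortfall in numbers costs about 0.4 points of power at the 0.0492 level (80.1% to 79.7%). These figures assume the planned rates of 20.4% and 16.7%, a look at exactly half the information, and two-sided levels.

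The point should be corrected before results are seen, because a confirmatory trial needs one threshold and a stated size that the design delivers.

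**What to change.** 1. In protocol 10.4 and SAP 8.5.5, state which hypothesis and direction 0.0054 tests, whether it is one- or two-sided, and whether crossing it can support a non-inferiority claim. Align protocol 9.5 and SAP 8.5.1 and 8.5.3 with that statement.
   - If it can: use a pair that holds 0.025 (0.0052/0.0480 or 0.0031/0.0490), and put the matching final interval (95.2% or 95.1%) in the risk-difference rule.
   - If it cannot: keep the 95% interval, and delete the 0.0492 adjustment and the step from 313 to 315.
2. Use the same interval level in SAP 9 and 10.1, and reconcile the odds-ratio interval there with the 5-point margin, for example by making the protocol's risk-difference interval the deciding one. Changing the confidence level alone gives no usable rule in the SAP.
3. Keep 693 and state that it leaves about 624 evaluable patients if all 10% are lost, with power of 79.9% at 0.05, 79.7% at 0.0492 or 0.0490, or 79.4% at 0.0480. Alternatively, restate the drop-out allowance as about 9%.
4. In SAP 8.1, start the final analysis when all randomised patients have reached day 30 or left the study.
5. In the same edit, reconcile the other totals still in the documents: 678 in the synopsis and SAP 8.3.1, 690 in SAP 7 and 9.1, and 308 per arm in the SAP baseline table.

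The cost is wording only. No patients are added, and the stated power falls by at most about half a point.

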### 4.4 Sample size calculation

In international literature there is scarce information about the percentages of treatment failure in patients admitted with an AECOPD receiving usual care. Therefore, we have performed a further search on PCT studies with a primary outcome of 30-day treatment failure. In the study by Schuetz et al. (JAMA 2009), who studied patients with lower respiratory tract infection, 30-day treatment failure was observed in 15.5% of the patients randomised to biomarker-based treatment, as compared to 18.9% in those randomised to usual care. This implies a relative risk of 0.82 in favour of the biomarker-based strategy. The study by Schuetz et al. was designed as a non-inferiority study, using a non-inferiority boundary of 7.5%. In view of these data we decided to design our study as a non-inferior study, whereas we choose a non-inferiority boundary of 5.0%. We based the primary outcome on the study of Huang et al. (NEJM 2018) (15). The incidence of the primary outcome was 20.4%. Using the relative risk of 0.82 in favour of the PCT-guided treatment group we expect the incidence of the primary outcome to be 16.7% in the PCT-guided treatment group. Then a total sample size of 626 is required (313 per treatment arm) to demonstrate non-inferiority with a power of 80%, and applying a one-sided alpha error of 0.025. We aim to enroll a total of 690 patients, accounting for a 10% drop-out rate. Because of an interim-analysis this number of patients will increase to 693 (as detailed below in section 10.4).

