### **10. STATISTICAL ANALYSIS**

There will be two analysis populations for this study:

1. The Intention-to-Treat (ITT) population is defined as all randomised patients who took at least one dose of study drug.
2. The Per-Protocol (PP) population is defined as a subset of ITT population constituted by those patients who: a) met all inclusion/exclusion criteria, b) attained a sufficient compliance to the treatment received, treatment with prednisolone and/or antibiotics, when prescribed on admission for at least 5 days, and c) did not present serious deviations from the protocol.

The analysis of all the efficacy variables will be performed on both the ITT and the PP populations in order to assess the robustness of the findings from the ITT population. All the demographic and baseline patients' characteristics and safety outcomes will be analysed using the ITT population.

All efficacy variables will be analysed for ITT and the PPS, and the PP population will be considered the primary population for assessing efficacy.

---

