The quality of life endpoints, using the COPD Assessment Test (CAT) and the EXACT-respiratory symptoms questionnaire, consist of multiple (three) measurements per subject. These measurements are all performed on the same time point (baseline, day 10 and day 30). These endpoints will be scored using the mean score and standard deviation when normally distributed and a median with the inter quartile range when the data have a skewed distribution. These data will be analyzed with a mixed effects model with random effects for center and patient to account for the extra hierarchical level in the data. The residuals will be evaluated for normality to test the assumptions of the models. In case of violations, transformations will be conducted on the dependent variable.

The unpaired continuous variables will be reported using the mean score and the standard deviation (normal distribution) or the median with the inter quartile range (skewed distribution). These variables will be analyzed using an mixed effects model.

The frequency and percentage will be reported for the categorical (mostly dichotomous) variables. Analysis of these variables will be performed using a logistic mixed-effects model.

- The analysis populations upon which the tables and figures will be based will be the per-protocol analysis population.

Table 2. Primary endpoint and secondary endpoints

	PCT-guided treatment (n = 315)	Usual care (n = 315)		p-value
Primary endpoint:				
Overall treatment failure:	n (%)	n (%)	OR (95% CI)	
- Disease-related mortality	n (%)	n (%)		
- Endotracheal intubation	n (%)	n (%)		
- Vasopressors	n (%)	n (%)		
- Renal failure	n (%)	n (%)		
- Lung abscess/empyema	n (%)	n (%)		
- Pneumonia development	n (%)	n (%)		
- Hospital readmission	n (%)	n (%)		
Secondary endpoints				
Incomplete resolution of the clinical signs and symptoms at day 30 after (scored using the modified Anthonisen criteria)	n (%)	n (%)	OR (95% CI)	

Change in QoL using the CAT: after 10 days after 30 days	mean (SD)or median [IQR]	mean (SD)or median [IQR]		
Start of antibiotic therapy after an initial opposite decision (after 48 hours)	n (%)	n (%)	OR (95% CI)	
Side effects (gastro-intestinal complaints, allergic reactions)	n (%)	n (%)	OR (95% CI)	
Cumulative antibiotic consumption	mean/median days (SD) or [IQR]	mean/median days (SD) or [IQR]		
Cumulative prednisolone consumption	mean/median days (SD) or [IQR]	mean/median days (SD) or [IQR]		

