9.3 Protocol Deviations

When a physician decides to prescribe antibiotic therapy even though the patient has a low serum concentration of procalcitonin ($\leq 0.25 \mu\text{g/mL}$) this leads to a protocol violation. The patient might recover because of the antibiotic therapy instead of still experiencing symptoms on day 30, which could directly impact the primary endpoint. This subject should not be analyzed in the per protocol analysis, because of this major protocol deviation/violation.

Early termination of antibiotic therapy, in both groups, could have an impact on the primary endpoint. This could happen when a patient has an initial quick recovery and gets discharged from the hospital without antibiotic therapy and then has a relapse. We do not expect this to happen more in one of the two treatment arms, although a high PCT might lead to less frequent discontinuation of the treatment when the patient is discharged in the first 5 days (the antibiotic therapy should be given during 5 days in both groups).

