
25. ZonMW. Budget Impact Analyses in de praktijk. Leidraad Budget Impact analyse [Internet]. 2020 Feb. Available from: www.facebook.com/zonmwNL

17 Listing of Tables, Listings and Figures

Tables:

- Table 1:
 - Title: Baseline characteristics
 - 3 columns, at least twelve rows
 - Per-protocol population will be given, since this is the primary analysis population
 - Mean will be reported with one decimal, just as the standard deviation and range
 - Median will be reported with one decimal
 - Frequencies will be reported in rounded numbers
 - Percentages will be reported after the frequency as (%) with one decimal
 - Interquartile range will be reported after the median as [IQR] with one decimal

- Table 2:
 - Title: Primary endpoint and secondary endpoints
 - 5 columns, 14 rows
 - Per-protocol population will be given, since this is the primary analysis population
 - Frequencies will be reported in rounded numbers
 - Percentages will be reported after the frequency as (%) with one decimal
 - Interquartile range will be reported after the median as [IQR] with one decimal
 - Adjusted odds ratio/RR/RD will be reported with 2 decimals
 - 95% C.I. will be reported with 2 decimals
 - P-value will be reported with 3 decimals
 - Mean/median value of the CAT and EXACT will be reported with one decimal, just as the standard deviation or the interquartile range[IQR]

- Table 3:

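### The 80% power applies to 315 per arm in a per-protocol primary analysis, but the inflation to 693 covers only drop-out and makes no stated allowance for per-protocol exclusions

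*Protocol*

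**What the plan says.** Protocol section 10 defines two populations and states that "the PP population will be considered the primary population for assessing efficacy". The primary analysis text later in that section, and SAP 8.2.3, 8.5.4, 10 and 10.2.1, say the same.

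Protocol 4.4 sizes the trial at 313 per arm for 80% power at one-sided 0.025. The control rate comes from a published PCT trial ("The incidence of the primary outcome was 20.4"%), and "we expect the incidence of the primary outcome to be 16.7% in the PCT-guided treatment group". The margin is 5 percentage points. Protocol 10.4 and SAP 8.5.5 raise the number to 315 per arm because the final two-sided level becomes 0.0492, and then inflate once: "Using a 10% drop-out rate this will lead to a total number of patients of 693".

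The PP set (Protocol section 10, SAP 8.2.2) keeps only patients who satisfied every eligibility criterion, were sufficiently compliant with the treatment prescribed at admission, and had no serious deviation. SAP 9.3 adds a specific case, a low-PCT patient who is nevertheless given antibiotics: "This subject should not be analyzed in the per protocol analysis, because of this major protocol deviation/violation".

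Neither document gives an expected PP exclusion rate or a power for the PP analysis under such exclusions.

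**The concern.** A sample size is a requirement for the set that is analysed. Here that is the PP set, so the 315 per arm must remain after every loss that the PP definition imposes. The allowance between 630 and 693 is labelled drop-out only. A patient who is treated against the PCT result, or found ineligible after randomisation, can have complete day-30 data and still leave the primary analysis. A drop-out allowance does not describe that kind of loss.

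The PP interval is the one compared with the 5-point margin. If the PP set falls below 315 per arm, the interval is wider than planned and an inconclusive result is more likely than the stated 20%. Anyone reading the plan would take 80% as the power of the decisive analysis without seeing the condition attached to it.

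**Working it through.** **Inputs**
- Failure rates 20.4% (usual care) and 16.7% (PCT-guided), and margin 5 points: Protocol 4.4 and SAP 7.
- Final level 0.0492 two-sided, that is 0.0246 one-sided; 315 per arm; 693 in total: Protocol 10.4 and SAP 8.5.5.
- PP exclusion rate: not given, so a range is used.

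**Formulas** (risk difference, unpooled variance)
- Distance from the margin: 0.05 + (0.204 − 0.167) = 0.087.
- Variance term: V = 0.167 × 0.833 + 0.204 × 0.796 = 0.1391 + 0.1624 = 0.3015.
- n per arm = (z₁₋α + z₀.₈)² × V / 0.087².
- Power at n per arm = Φ(0.087 / √(V/n) − z₁₋α).

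**Reproducing the plan**
- One-sided 0.025: (1.960 + 0.842)² × 0.3015 / 0.087² = 312.6, so 313. This matches.
- One-sided 0.0246: (1.967 + 0.842)² × 0.3015 / 0.087² = 314.2, so 315. This matches.
- Power at 315 per arm: Φ(0.087/0.03094 − 1.967) = Φ(0.845) = 80.1%.
- Enrolment: 2 × 315 × 1.10 = 693. This matches.

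**Break-even**
693 randomised is 346.5 per arm. The largest total loss that leaves 315 per arm is 1 − 315/346.5 = 9.1%.

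**Power by total loss from 693 (drop-out and PP exclusions together, equal in both arms)**

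| Total loss | n per arm | Power |
|---|---|---|
| 0% | 346.5 | 83.7% |
| 10% | 311.9 | 79.7% |
| 15% | 294.5 | 77.4% |
| 20% | 277.2 | 74.9% |
| 25% | 259.9 | 72.2% |
| 30% | 242.6 | 69.2% |

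**Power if the full 10% drop-out occurs first (311.9 per arm) and PP exclusions follow (assumed rates)**

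| PP exclusions | n per arm | Power |
|---|---|---|
| 5% | 296.3 | 77.7% |
| 10% | 280.7 | 75.4% |
| 15% | 265.1 | 73.0% |
| 20% | 249.5 | 70.4% |

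Overrides of a low PCT can occur only in the PCT arm, because usual-care results stay blinded. If, as an assumption, all PP exclusions fell in that arm and left 315 in usual care, power would be 78.1% at 10% excluded and 75.7% at 20%.

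This is a different question from how to inflate for 10% drop-out. Dividing by 0.9 gives 630/0.9 = 700, and a 10% drop-out then leaves exactly 315 per arm, again with nothing for PP exclusions.

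**The case against.** A reader might infer that the PP set will certainly be smaller than 315 per arm, or that power will fall to 70–75%. The documents support neither. They give no exclusion rate, and 70–75% needs roughly 11–21% exclusions on top of a full 10% drop-out. If actual drop-out is lower, the unused allowance absorbs PP exclusions. There are reasons it might be lower: both documents commit to every effort to collect the primary endpoint, Protocol 8.6 keeps following withdrawn patients where consent allows, and SAP 8.4 plans multiple imputation under MAR or MCAR. The categories can also overlap, since a patient who withdraws may also be non-compliant. And drop-out is never defined, so the sponsor may have meant 10% to cover every loss; power would then be 79.7%.

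A reader might also take the header of SAP Table 2, a PP table showing 315 per arm, as proof that the plan assumes no PP exclusions. It is too weak for that. SAP 17 assigns Table 1 to the PP population as well, and its header shows 308 per arm, which corresponds to the 678 total still found in the Protocol synopsis and SAP 8.3.1 (2 × 308 × 1.1 = 677.6). The headers look like placeholders from different stages. SAP 9.3 is likewise conditional: it gives no frequency of overrides, and its paragraph on early antibiotic stops does not itself exclude those patients.

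All of this limits how large a shortfall can be claimed. None of it supplies an allowance for PP exclusions. Imputation replaces missing outcomes; it does not return patients removed for deviations.

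**Conclusion.** The point holds in conditional form. The sample-size arithmetic is correct, and 80.1% at 315 per arm reproduces. The gap is that the 80% is stated without its condition: for the PP analysis, drop-out and PP exclusions must together be at most about 9% of the 693. Beyond that, the shortfall is about 3 points at 15% total loss, 5 at 20%, 8 at 25% and 11 at 30%.

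These figures assume the plan's 3.7-point benefit, equal losses in both arms, event rates unchanged by exclusion, and the Protocol's risk-difference comparison with the 5-point margin. The SAP's decision on an odds-ratio interval was not evaluated here. No particular loss rate can be read from the documents, so no single reduced power should be quoted as the expected one.

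**What to change.** In Protocol 4.4 and 10.4 and SAP 7 and 8.5.5:

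- State that the 80% applies to 315 per arm in the PP set.
- Give the condition: with 693 randomised, 80% power requires drop-out plus PP exclusions of at most about 9% in total; power is about 77% at 15%, 75% at 20% and 69% at 30%.
- Give separately the power of the ITT analysis as the plan defines it (randomised, at least one dose of study drug): about 80% with 10% missing, and up to about 84% if all 693 are analysed.

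This is a change of wording only, with no extra enrolment. The cost is a less favourable stated power for the primary analysis.
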